## 6.6 ADVERSE EVENTS AND SERIOUS ADVERSE EVENTS

### 6.6.1 DEFINITION OF ADVERSE EVENTS

The National Institutes of Health follows OHRP guidance on the definitions of adverse events and the associated reporting expectations. Thus, an adverse event is defined as any untoward or unfavorable medical occurrence in a human subject, including any abnormal sign, symptom, or disease, temporally associated w/ subject's participation in research, whether or not considered related to subject's participation in the research; encompasses both physical and psychological harm. This study will also capture non-medical events that may be behavioral (i.e., self-harm) or social (e.g., child protective services involvement with the family).

### 6.6.2 DEFINITION OF SERIOUS ADVERSE EVENTS

According to the SDSU Human Research Protection Program and OHRP guidance, **(from SDSUHRPP Standards and Practices v. 02.13.19; also definition in OHRP guidance, which NIH follows)**, an adverse event is considered serious if it: 1) Results in death; 2) is life

threatening; 3) requires inpatient hospitalization; 4) results in persistent or significant disability or incapacity; 5) results in congenital anomaly or birth defect; or 6) risks the subject's health and may require medical or surgical intervention to prevent one of the outcomes listed above. For the purpose of this study, hospitalization is defined as an inpatient hospital stay equal to or greater than 24 hours (inclusive of ER visits of 24 hours or longer).

---

### 6.6.3 CLASSIFICATION OF AN ADVERSE EVENT

#### 6.6.3.1 SEVERITY OF EVENT

The Principal Investigators, in consultation with physician Co-Investigator [name] and other Co-Investigator [name], if necessary, will assess the severity of adverse events as either: 1) Grade 1: Mild; 2) Grade 2: Moderate; 3) Grade 3: Severe; 4) Grade 4: Life threatening; or 5) Grade 5: Death. The following definitions will be used to assign a severity rating:

1. **Grade 1 Mild:** asymptomatic or mild symptoms; clinical or diagnostic observations only; no intervention indicated.
2. **Grade 2 Moderate:** minimal, local or noninvasive intervention indicated; limiting age-appropriate instrumental activity of daily living.
3. **Grade 3 Severe or medically significant but not immediately life-threatening:** hospitalization or prolongation of hospitalization indicated; disabling; limiting self-care activities of daily living.
4. **Grade 4 Life-threatening consequences:** urgent intervention indicated.
5. **Grade 5 Death related to adverse event.**

Because the study focuses on suicide prevention, adverse events related to suicidal ideation, suicidal behaviors, and other types of self-harm will be graded for severity using the following guidelines:

#### **Grade 1:**

1. Worsening of suicidal ideation from baseline or last assessment

#### **Grade 2:**

1. Development of new suicide intention or plan
2. Engaging in self-harm behaviors which do not require hospitalization
3. Engaging in self-harm behaviors which require an ER visit but not inpatient hospitalization

#### **Grade 3:**

1. Suicide attempt or other type of self-harm which requires hospitalization but is not immediately life threatening.
2. Suicide attempt or other type of self-harm which is disabling
3. Suicide attempt or other type of self-harm which limits self-care activities of daily living

#### **Grade 4:**

1. Suicide attempt or other type of self-harm which is life threatening and requires urgent intervention

**Grade 5:**

1. Death by suicide
2. Death from another type of self-harm
3. Death from any cause

---

**6.6.3.2 RELATIONSHIP TO STUDY INTERVENTION/EXPERIMENTAL MANIPULATION**

Adverse events may be caused by one or more of the following:

1. the procedures involved in the research;
2. an underlying disease, disorder, or condition of the subject; or
3. other circumstances unrelated to either the research or any underlying disease, disorder, or condition of the subject.

In general, adverse events that are determined to be at least partially caused by (1) would be considered related to participation in the research, whereas adverse events determined to be solely caused by (2) or (3) would be considered unrelated to participation in the research.

All adverse events will be rated by the Principal Investigators (in consultation with physician study Co-Investigator [name] and other Co-Investigator [name], if necessary) on the degree to which they are related to the study intervention using the following attribution scale and definitions:

1. **Not related:** The adverse event is clearly not related to the study intervention.
2. **Unlikely related:** The adverse event is doubtfully related to the study intervention.
3. **Possibly related:** The adverse event may be related to the study intervention.
4. **Probably related:** The adverse event is likely related to the study intervention.
5. **Definitely related:** The adverse event is clearly related to the study intervention.

In considering the degree to which the adverse event is related to the intervention, the Principal Investigators and Co-Investigators will consider:

1. Whether the adverse event is a known reaction of the intervention?
2. Whether the adverse event is similar to other adverse events listed in the study protocol and consent documents?
3. Whether the adverse events occurred before in this study?
4. Whether the adverse event is reasonably temporally related to the intervention?
5. Whether the adverse event was present at the baseline assessment of the participant?
6. Whether the adverse event can be reasonably explained by the participant's clinical disease status?
7. Whether there are any other potential causes for the adverse event?

---

**6.6.3.3 EXPECTEDNESS**

The Principal Investigators (in consultation with physician study Co-Investigator [name] and other Co-Investigator [name], if necessary) will be responsible for determining whether an

adverse event (AE) is expected or unexpected. The following definition will be used to determine the expectedness of the AE:

OHRP defines *unexpected adverse event* as any adverse event occurring in one or more subjects participating in a research protocol, the nature, severity, or frequency of which is **not** consistent with either:

1. the known or foreseeable risk of adverse events associated with the procedures involved in the research that are described in (a) the protocol-related documents, such as the IRB-approved research protocol, any applicable investigator brochure, and the current IRB-approved informed consent document, and (b) other relevant sources of information, such as product labeling and package inserts; or
2. the expected natural progression of any underlying disease, disorder, or condition of the subject(s) experiencing the adverse event and the subject's predisposing risk factor profile for the adverse event.

According to OHRP's unanticipated problems involving risks and adverse events guidance (2007), the vast majority of adverse events occurring in the context of research are *expected* in light of (1) the known toxicities and side effects of the research procedures; (2) the expected natural progression of subjects' underlying diseases, disorders, and conditions; and (3) subjects' predisposing risk factor profiles for the adverse events.

By the definition above, the following adverse events are expected for the study: non-suicidal self-injury, suicidal ideation, suicidal intent, suicidal plan, suicide attempts, hospitalization related to suicide attempt or self-harm, and death from suicide or self-harm. Additionally, given that SGM youth (particularly those with a history of suicide attempts and ideation) experience elevated health disparities compared to the general population on many mental health/substance use markers, we also expect significant comorbidities, including psychiatric and substance use disorders, to be reported over the course of the study.

All adverse events will be rated on whether or not they were *expected* (Yes, No) according to OHRP criteria and in consideration of the adverse events expected for this study.

---

#### 6.6.4 TIME PERIOD AND FREQUENCY FOR EVENT ASSESSMENT AND FOLLOW-UP

Adverse events will be ascertained by the following methods: 1) spontaneously reported symptoms; 2) observed symptoms and signs; 3) other people's reports (e.g., parent, guardian, health care provider, child protective services, trusted adult); and through 4) regular assessments using validated questionnaires. The University of Washington Risk Assessment Protocol (UWRAP) will be administered during each major assessment session (Case Series: baseline, 3-month follow-up; Open Trial: baseline, 3-month follow-up, 6-month follow-up). The Columbia-Suicide Severity Rating Scale (C-SSRS) will also be administered during each major assessment session and at the beginning of each virtual, phone, or in person intervention session, to assess suicidal ideation, intent, plans, and behaviors. The UWRAP and C-SSRS are being utilized to identify suicide-related AEs and SAEs. All staff interacting with study participants will be trained to observe participants for signs of injury or illness during virtual and in person assessments. If any injury or illness appears to be related to child abuse and neglect, study staff will also follow the standard of practice for child abuse and neglect, in addition to

documenting an adverse event. Study staff will also be trained to document spontaneously reported symptoms or other information about adverse events when reported by a participant or another person. If the adverse event is reported to the study team by another person, a member of the study team will attempt to verify the adverse event by contacting the study participant. Suicidality-related clinical worsening is not solely defined by increases in C-SSRS scores. Clinical worsening is determined on a case-by-case basis by the Principal Investigators, if needed in consultation with Drs. [name] and [name].

#### 6.6.5 ADVERSE EVENT REPORTING

The Principal Investigators are responsible for reporting adverse events to the SDSU IRB according to the timelines established in the IRBs reporting policies and will be assisted in submitting reports by the research coordinator. For all adverse events that are deemed expected and/or unrelated to the study, a summary should be submitted to the NIMH PO with the annual progress report. Adverse events that are not SAEs will be included in the DSMB full data report that is submitted once a year.

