#### 6.6.6 SERIOUS ADVERSE EVENT REPORTING

The Principal Investigators are responsible for reporting serious adverse events to the SDSU IRB according to the timelines specified by the IRBs reporting policies and will be assisted in submitting reports by the research coordinator. According to SDSU IRB policy, all study-related serious adverse events must be reported to SDSU IRB within 24 hours. A summary of serious adverse events that are deemed expected and/or unrelated to the study will be submitted to the NIMH PO with the annual progress report. Unexpected Serious Adverse Events related to study participation will be reported to the NIMH PO within 10 business days of the study team becoming aware of the serious adverse event. SAEs will be reported to the DSMB in the data reports submitted three times a year. Expedited reporting will be provided to the Board for all deaths and unexpected and related SAEs. For deaths, the report will be submitted within 5 business days, and for unexpected and related SAEs, the report will be submitted within 10 business days.

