#### 8.1.6 SAFETY OVERSIGHT

Safety oversight will be under the direction of a NIMH Data and Safety Monitoring Board (DSMB) composed of individuals with the appropriate expertise, including, at minimum, one content-related or therapeutic area expert and a biostatistician. Members of the DSMB will be independent from the study conduct and free of conflict of interest. The board will meet via teleconference 3 times per year. The DSMB will operate under the rules of an approved charter that clearly outlines what data points will be monitored, how the data will be monitored, and the monitoring schedule. The DSMB review will include, at minimum: enrollment data, safety data, and data and protocol

integrity. These will be provided to the Board for review in advance of each meeting. Any DSMB member can request an additional meeting or additional information should they desire it. The DSMB will issue meeting minutes that will be provided to the Principal Investigators following each review/meeting. This report will include any significant actions taken and the final recommendations with regard to the study's continuation. These reports will be submitted to the NIMH Program staff in the annual progress report.

---

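### A suicide attempt that meets no SAE criterion is assured of routine DSMB reporting only once a year, and section 8.1.6 does not say that it is part of the safety data for the three yearly meetings

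*Combined protocol and SAP*

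**What the plan says.** **Routine reporting to the board.** Section 6.6.5: "Adverse events that are not SAEs will be included in the DSMB full data report that is submitted once a year". Section 6.6.6: "SAEs will be reported to the DSMB in the data reports submitted three times a year". Section 6.6.6 also provides expedited board reports for all deaths (5 business days) and for SAEs that are both unexpected and related (10 business days).

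**What counts as serious.** Section 6.6.2 gives six criteria, and none names a suicide attempt. Two matter most here. For the inpatient criterion, "hospitalization is defined as an inpatient hospital stay equal to or greater than 24 hours", with emergency-room stays of that length included. Under the sixth criterion, an event is serious if it "risks the subject's health and may require medical or surgical intervention to prevent one of the outcomes listed above".

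**Severity grading.** In section 6.6.3.1, Grade 2 includes "Engaging in self-harm behaviors which require an ER visit but not inpatient hospitalization". The non-fatal lines that name a suicide attempt are in Grades 3 and 4. They tie it to hospitalization, disability, limits on self-care, or threat to life.

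**Expectedness.** Section 6.6.3.3 lists suicide attempts among the events expected in this study.

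**Board meetings.** Under section 8.1.6 the DSMB meets three times a year and receives material before each meeting. "The DSMB review will include, at minimum: enrollment data, safety data", together with data and protocol integrity. "The DSMB will operate under the rules of an approved charter that clearly outlines what data points will be monitored". "Any DSMB member can request an additional meeting or additional information should they desire it".

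**The concern.** The reporting schedule turns on whether an event is serious, and in this trial that line can run through the middle of the outcome the intervention is meant to reduce. A hospitalized attempt goes to the board in the next of three yearly reports. An attempt that meets no SAE criterion is promised only in the yearly full report.

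The trial has one arm, so the board has no concurrent comparison. To judge whether attempts are accumulating faster than expected, it relies mainly on the count. As written, it is assured of the serious part of that count at each review and of the rest once a year.

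The faster routes are conditional. Because attempts are already listed as expected, quicker reporting of a non-SAE attempt depends on an investigator judging it to be an unanticipated problem, on a board member asking, or on charter wording that cannot be seen here.

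The concern is limited to routine review by the independent board; participants are still monitored. The C-SSRS is given at every intervention session and major assessment (section 6.6.4). The Principal Investigators rate every adverse event, and the IRB receives events on its own timelines.

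**Working it through.** The plan gives no figure to reproduce. The check reads the reporting routes together and then works out the timing they imply.

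**Step 1: routes open to a non-SAE attempt**

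| Route | Section | Assured and routine? |
|---|---|---|
| Annual full data report | 6.6.5 | Yes, once a year |
| SAE data reports, three a year | 6.6.6 | No, SAEs only |
| Expedited report | 6.6.6 | No, deaths and unexpected, related SAEs only |
| Unanticipated problem, 10 business days | 6.7.1, 6.7.2 | No. It must be unexpected, at least possibly related, and suggest greater risk |
| Request by a board member | 8.1.6 | No, at the member's initiative |
| Safety data at each meeting | 8.1.6 | Not stated; the term is undefined |

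Section 8.1.9 also refers to an annual full data report, for protocol deviations. This supports reading the other two yearly reports as shorter.

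**Step 2: can such an attempt exist?** Yes. Inclusion criterion 8 (section 4.1) counts actual and interrupted attempts, and an interrupted attempt may cause no injury. The adverse event section does not define an attempt. The grading does not settle the matter, because grade is not seriousness. How many attempts would fall in this class cannot be estimated from the documents.

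**Step 3: inputs for timing**
- Reports: 1 a year against 3 a year, so gaps of 12/1 = 12 and 12/3 = 4 months. Even spacing is assumed.
- Open-trial accrual: 5 a month for 6 months, N = 30 (section 4.4), with 6 months each. Total participant-time is 30 × 6 = 180 person-months.
- Open-trial duration: 15 months (synopsis).
- First report after the trial opens: T uniform on (0, gap). This assumes that report dates are unrelated to the trial's start.

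**Step 4: wait for an event.** Uniform on (0, gap).
- Gap 12: maximum 12, mean 12/2 = 6 months.
- Gap 4: maximum 4, mean 4/2 = 2 months.

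If the annual report coincides with one of three evenly spaced meetings, the assured non-SAE listing is 0, 4 and 8 months old at the three meetings.

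**Step 5: trial progress before the first report**
- Probability that all 30 are enrolled, P(T > 6): gap 12, 1 − 6/12 = 0.50; gap 4, 0.
- Mean number enrolled, E[min(30, 5T)]: gap 12, 0.5 × 15 + 0.5 × 30 = 22.5; gap 4, 5 × 2 = 10.
- Share of planned participant-time elapsed. For T ≤ 6, the elapsed amount is 5T²/2 person-months. Gap 4: E[T²] = 4²/3 = 16/3, so 2.5 × 16/3 = 13.3, and 13.3/180 = 0.074. Gap 12: accrual and exit mirror each other about month 6, so the mean share is 0.50.

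**Step 6: reports in 15 months**
- Gap 12: a second report falls inside if T ≤ 3, with probability 3/12 = 0.25. That gives 1 or 2 reports, mean 15/12 = 1.25.
- Gap 4: a fourth report falls inside if T ≤ 3, with probability 3/4 = 0.75. That gives 3 or 4 reports, mean 15/4 = 3.75.

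The 5-month case series would contain 0 or 1 annual reports, against 1 or 2 four-monthly reports.

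**The case against.** **The charter may settle it.** The protocol leaves the monitored data points and schedule to an approved charter. If that charter requires every attempt at each meeting, only a difference in wording remains. This stands as a limit. It does not remove the point, because section 6.6.5 states a slower rule of its own.

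**Sections 6.6.5 and 8.1.6 can both be true.** Section 6.6.5 does not say that non-SAE events appear only in the annual report, and safety data could cover all adverse events. That reading is possible. The contrast with section 6.6.6 and the label of a full report point the other way, and a reader cannot tell which is meant.

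**An excess of attempts has its own route.** Unexpectedness covers frequency as well as nature and severity. Attempts occurring more often than foreseen, at least possibly related and suggesting greater risk, would go to the board within 10 business days as an unanticipated problem. This is the strongest point, but that route starts with the investigators' judgement, whereas routine listing would let the board form its own.

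**The affected class may be small or empty.** The sixth SAE criterion is broad, and the grading lines that name attempts largely parallel the SAE criteria. This stands; no number of attempts is claimed.

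**The timing figures look more precise than they are.** The documents give neither the spacing of the reports nor their offset from trial start. The comparison of about 12 with about 4 months carries the point, and the other figures only illustrate it.

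**Tiered reporting is ordinary.** Reporting serious events more often than non-serious ones is common. It suits this trial less well because the event in question is the one the intervention is meant to prevent.

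**Conclusion.** The concern holds and should be addressed; confidence is moderate. The only routine board reporting that the protocol assures for a non-SAE suicide attempt is annual, and section 8.1.6 does not say that such attempts belong to the safety data for the three yearly meetings.

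The assured wait is up to 12 months against up to 4 for an SAE, so a whole 3- or 6-month participation could fall between two annual reports. Under the stated assumptions, half of the planned open-trial participant-time would on average have passed before the first report that must include these attempts, against about 7% with four-monthly reports.

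These timing results rest on evenly spaced reports, report dates unrelated to the trial's start, and accrual as planned. They do not depend on the number of attempts, which is unknown. It does not follow that the board will in fact see such attempts only once a year: the charter, the sixth SAE criterion, the unanticipated-problem route or a member's request could each bring them forward.

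**What to change.** In section 6.6.5, add one sentence: every actual or interrupted suicide attempt, whatever its seriousness, grade or expectedness, is listed in the DSMB data report submitted three times a year. Inclusion criterion 8 already draws the line at actual and interrupted attempts. Using the same line here would also give the adverse event section the definition it lacks; the team should confirm that it suits safety reporting.

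Define safety data in section 8.1.6 to match, and check that the charter agrees. If the charter already requires this listing, say so in section 6.6.5.

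The cost is small: one sentence, a check of the charter wording, and some added rows in a report that is already produced. The C-SSRS and the adverse event log already capture these events, so no new data collection is needed.

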#### 6.6.6 SERIOUS ADVERSE EVENT REPORTING

The Principal Investigators are responsible for reporting serious adverse events to the SDSU IRB according to the timelines specified by the IRBs reporting policies and will be assisted in submitting reports by the research coordinator. According to SDSU IRB policy, all study-related serious adverse events must be reported to SDSU IRB within 24 hours. A summary of serious adverse events that are deemed expected and/or unrelated to the study will be submitted to the NIMH PO with the annual progress report. Unexpected Serious Adverse Events related to study participation will be reported to the NIMH PO within 10 business days of the study team becoming aware of the serious adverse event. SAEs will be reported to the DSMB in the data reports submitted three times a year. Expedited reporting will be provided to the Board for all deaths and unexpected and related SAEs. For deaths, the report will be submitted within 5 business days, and for unexpected and related SAEs, the report will be submitted within 10 business days.

### 6.7 UNANTICIPATED PROBLEMS

#### 6.7.1 DEFINITION OF UNANTICIPATED PROBLEMS

This protocol uses the definition of Unanticipated Problems as defined by the Office for Human Research Protections (OHRP):

OHRP considers *unanticipated problems*, in general, to include any incident, experience, or outcome that meets **all** of the following criteria:

1. unexpected (in terms of nature, severity, or frequency) given (a) the research procedures that are described in the protocol-related documents, such as the IRB-approved research protocol and informed consent document; and (b) the characteristics of the subject population being studied;
2. related or possibly related to participation in the research (in this guidance document, *possibly related* means there is a reasonable possibility that the incident, experience, or outcome may have been caused by the procedures involved in the research); and

3. suggests that the research places subjects or others at a greater risk of harm (including physical, psychological, economic, or social harm) than was previously known or recognized.

Unanticipated problems can include experiences such as protocol deviations, data breaches, having study-related data or documentation unsecured and stolen.

---

